2 STUDY RATIONALE

2.1 Rationale for Gallium Treatment in CF Patients

Gallium nitrate is a promising therapeutic for CF airway infections for a number of reasons.

A large proportion of infecting organisms in CF airway infections are living in biofilms. Gallium nitrate could deliver "multiple hits" against infecting bacteria. At low concentrations, it blocks biofilm formation and inhibits bacterial growth; at higher concentrations, it kills planktonic and biofilm bacteria (17).

Gallium exhibits antimicrobial properties against laboratory *P. aeruginosa* strains and against mucoid and non-mucoid clinical isolates from CF patients. The vast majority of antibiotic resistant *P. aeruginosa* strains that we have tested so far are also susceptible to gallium (17).

Microbial resistance to gallium may be difficult for *P. aeruginosa* to acquire because gallium substitutes for iron in some metabolic processes and iron is an essential nutrient that is avidly taken up by bacteria. We have shown that mutations in three different iron uptake systems of *P. aeruginosa* did not change susceptibility to anti-biofilm or growth inhibitory actions of gallium (17). This suggests that multiple different iron uptake pathways can mediate the effects of gallium.

If resistance to gallium develops via mutation of gallium targets, it may not compromise the effectiveness of conventional anti-pseudomonal antibiotics currently in use. This is because gallium's antimicrobial mechanism differs from that of conventional antibiotics.

Laboratory data demonstrates that gallium's antimicrobial effect is enhanced in iron-limited conditions (17). Because bio-available iron is scarce in the lung (23), the antimicrobial action of gallium may be augmented *in vivo*. Thus, the concentrations of gallium required for efficacy in humans may be even lower than we have found *in vitro*.

Although *P. aeruginosa* is generally regarded as the most important pathogen in CF, patients also develop serious airway infections with other organisms including *Staphylococcus aureus* (methicillin sensitive and resistant strains), *Haemophilus influenzae*, and *Burkholderia cepacia* (24). Like *P. aeruginosa* infections, these organisms can be found in high concentrations in the sputum (3), develop antibiotic resistance (25;26), and can be difficult to treat with conventional antibiotics. Though evidence is incomplete, some of these organisms may live in biofilms in the CF sputum (27). Importantly, all of these organisms require iron for growth and thus they may also be sensitive to the antimicrobial action of gallium. Work by our group and others indicates that gallium nitrate has activity against *Stenotrophomonas maltophilia*, the *Burkholderia cepacia* complex, *Klebsiella pneumonia* (including ESB strains), *Escherichia coli*, *Acinetobacter baumannii*, *Bacillus anthracis*, *Francisella sp.* and *Salmonella typhi* (28).

Gallium may exhibit anti-inflammatory effects independent from the anti-microbial effect, which may be beneficial for CF lung infections. Extensive literature indicates that gallium has anti-inflammatory effects on various cells of the immune system and in intact animals. Gallium is a strong inhibitor of polyclonal and allo-antigen induced T-cell proliferation (29), and B-cell proliferation and antibody secretion (30). Gallium reduces Interleukin-6 (IL-6), Tumor Necrosis Factor- α (TNF- α), and nitric oxide release from lipopolysaccharide stimulated macrophage-like cells (31), and inhibits the expression of major histocompatibility complex and interferon- γ stimulated peritoneal macrophages (19).

Version 2.0 Version Date: 28 AUG 14 Page 18 of 57

In addition, we now have data from two non-blinded dosing cohorts in adults with CF noted in section 1.2 showing no evidence of toxicity but preliminary indications of clinical efficacy with improvement in both FEV_1 and FVC. We also found that although the PK did not correspond well to treatment response, the levels achieved in the sputum were similar to those used in *in vitro* experiments assessing the antimicrobial and anti-biofilm activity of gallium on *P. aeruginosa*. Here, we propose an initial proof of concept Phase 2 blinded efficacy study of gallium in CF patients using the maximum FDA-approved dose for patients with hypercalcemia (200 mg/m²/day for a 5 day infusion).

2.2 Risk / Benefit Assessment

No published studies exist that evaluate the safety of IV gallium nitrate in CF patients. However, there is extensive published information on the use of this compound over a wide range of doses both above and below the doses proposed in this trial in patients with both neoplastic as well as benign metabolic diseases. Moreover, this human experience extends over a period of more than 30 years, including a post-marketing experience of 17 years duration. Thus, the risks of the drug have been broadly described in thousands of patients and unique risks associated with the proposed dosing in CF patients would appear to be low. In this trial, we propose to limit our trial to stable CF subjects with normal renal function at a dose previously tested and shown to be safe in our Phase 1b CF study. Because of this, we anticipate potentially severe systemic adverse reactions to be unlikely.

A specific minimum human toxic dose has not been established. However, a "no effect" (placebo) dose of 0.05 mg/kg administered once per day subcutaneously was used in the randomized Phase 2 study in Paget's disease. A higher dose (0.5 mg/kg/d) demonstrated biological activity against markers of Paget's disease activity, but demonstrated no significant AEs. The lethal dose 50 (LD50) of gallium nitrate in mice is 4,360 mg/kg for oral doses and 600 mg/kg for subcutaneous doses (32). Renal toxicity is dose dependent and is usually the dose limiting adverse effect of parenteral gallium nitrate when administered by bolus injection or short (2 hours) IV infusion (2). Elevation of serum BUN and creatinine levels has been observed in approximately 12.5% of patients receiving recommended therapeutic doses of IV gallium nitrate (~ 400 mg/day for a typical adult). Toxicity depends on several factors: the total dose, the rate of administration, the underlying pathology, and use with other nephrotoxic drugs. Doses up to 1400 mg/m² by short IV infusion have been used in clinical trials. No significant toxicity has been observed at doses of 50 mg/m² (~ 100 mg for a typical adult) or less (33).

Nephrotoxicity occurs most commonly after large IV boluses are rapidly administered. While the exact mechanism of renal toxicity in humans is not known, studies in rats suggest that toxicity occurs when the influx of gallium into the circulation exceeds the ability of transferrin (or other binding proteins) to bind gallium (19;34). Unbound gallium forms gallate (Ga(OH)₄) which is rapidly excreted by the kidneys (35). Under conditions where gallate transiently reaches high levels, it is thought to precipitate within renal tubules and cause obstruction. Rats administered high levels of gallium nitrate developed flocculent complexes that were observed to be occluding the lumen of some renal tubules (34). X-ray energy spectrometry showed that gallium was found in the presence of calcium and phosphorus in the occluding precipitates (34).

This mechanism of renal toxicity is consistent with two additional observations. First, in rats and humans, osmotic diuresis significantly reduced the levels of gallium found in the urine and the incidence of renal toxicity when high doses were administered (34;35). Second, gallium

Version 2.0 Version Date: 28 AUG 14 Page 19 of 57

nephrotoxicity is markedly reduced by slow IV infusion or subcutaneous injection (19). These methods of delivery lower the rate at which gallium appears in the plasma, preventing transferrin saturation and reducing gallate delivery to the kidneys. Therapeutic doses of gallium have been administered to thousands of debilitated patients using slow infusions, without significant renal toxicity (36). If it occurs, renal toxicity is generally mild (transient proteinuria) at doses $< 300 \text{ mg/m}^2$ (21;22).

Hematological toxicity has also been observed with IV gallium nitrate, although this is generally mild and interpretation of this adverse effect is complicated by the fact that patients receiving gallium nitrate had malignancies, were hospitalized, and were undergoing frequent phlebotomy (19). In one study, 38% of gallium-treated cancer patients developed a greater than 3 gm/100mL drop in the hemoglobin level; however, only 18% of patients required a blood transfusion (22). Thrombocytopenia (platelet count< $150,000/\text{mm}^3$) occurred in 15% of patients and was most frequent at doses > $450 \text{ mg/m}^2/\text{day}$ (22). No bleeding was observed. Mild leukocytosis (mean increase of $0.9 \times 10^3/\text{mm}^3$) has also been observed in a dose dependent manner (22). These toxicities were not observed in our Phase 1b CF clinical trial.

Gallium can also produce hypocalcemia; treatment of hypercalcemia of malignancy is the approved indication for gallium. In rats, a single injection produces a rapid increase in urinary excretion of calcium; however, this is transitory and was subsequently shown to be an effect of concomitant diuresis rather than the drug itself (19). Several studies suggest that gallium lowers serum calcium levels in large part by inhibiting bone resorption (19;35;37;38). In patients without elevated blood levels of calcium, the reduction in calcium levels is usually mild and asymptomatic and can usually be treated with oral calcium supplements (39). These toxicities were not observed in our Phase 1b CF clinical trial.

Other AEs associated with gallium include optic neuritis (observed at high doses), tinnitus and mild high frequency hearing loss (apparent on audiograms), anorexia, nausea, diarrhea, stomatitis, conjunctivitis, lethargy, mild respiratory alkalosis with hyperchloremia, and rash (19). A reversible pulmonary syndrome consisting of dyspnea, rales, rhonchi, pleural effusion, and pulmonary infiltrates has been reported in association with gallium nitrate infusion, but this is rare and has occurred in patients with serious underlying malignant conditions. Thus the relationship of these other AEs and the pulmonary syndrome to the gallium infusion is uncertain (Ganite® (gallium nitrate injection) package insert,(21;40)). A case of pulmonary toxicity occurred in a patient receiving 300 mg/m²/day for seven (7) days every four (4) weeks (41). No pulmonary complaints were noted in our Phase 1b CF clinical trial; in fact, lung function improved with treatment.

2.3 Measures to Minimize Risk

All subjects will be instructed to ingest a minimum of two (2) liters of fluid per day during the five (5) day infusion of study drug (gallium nitrate or placebo) and for two (2) days thereafter to minimize the risks of nephrotoxicity. Fluid intake will be documented on a daily diary from Day 1 through Day 8. We will evaluate the respiratory status and general health of subjects before and after exposure to gallium. In the event of an allergic reaction during the six hour observation period on Day 1, adrenaline and anti-histamine will be immediately available. If needed, emergency services including an emergency room and medical ICU are immediately available in close proximity to the study site. Bronchospasm, if it occurs, will be treated immediately with nebulized albuterol. In addition, we will monitor the subject's physical exam, symptoms,

Version 2.0 Version Date: 28 AUG 14 Page 20 of 57

respiratory questionnaire results, spirometry, blood and urine clinical laboratory test results, and treat as indicated

The effects of gallium on an unborn child (fetus) are unknown and may be harmful. Women cannot participate if they are pregnant, are breast feeding, or plan to become pregnant during the study. Men cannot participate if they plan to father a child during the study.

There is no proven benefit of IV gallium in CF. However, the risks of the infusion dose proposed in this trial appear to be both low and well-defined in non-CF populations. In the future, IV gallium might be proved to be useful in the acute and chronic management of CF patients infected with *P. aeruginosa*.

3 STUDY OBJECTIVES

3.1 Primary Objective

To assess the efficacy of IV gallium to improve pulmonary function as measured by a 5% or greater relative improvement in FEV₁ from baseline to Day 28

3.2 Secondary Objectives

- To assess the safety and tolerability of IV gallium
- To assess the efficacy of IV gallium in improving measures of lung function including relative change in FEV₁ absolute change in FEV₁, and FVC
- To assess the efficacy of IV gallium in reducing *P. aeruginosa* in the lungs of CF patients based on quantitative cultures of sputum
- To assess the efficacy of IV gallium in improving respiratory symptoms as measured by the CF Respiratory Symptoms Diary -Chronic Respiratory Infection Symptom Severity Score (CFRSD-CRISS)
- To assess the sputum and blood PK profile of IV gallium
- To assess the rate of acquired resistance of *P. aeruginosa* to gallium
- To explore the anti-inflammatory properties of IV gallium
- To explore the efficacy of IV gallium in reducing the use of antibiotics for an acute indication

4 STUDY DESIGN

4.1 Study Overview

This is a phase 2, multi-center, randomized, double-blind, placebo-controlled trial in adults with CF chronically infected with *P. aeruginosa*. The study will evaluate the safety and clinical efficacy of a five-day infusion of IV gallium nitrate. Approximately one hundred twenty eligible subjects will be randomized in equal allocation to receive either a single 5-day infusion of IV gallium or volume-matched placebo. Subjects will be randomized using an adaptive randomization scheme to prevent imbalances in treatment allocation within baseline FEV₁ strata.

Version 2.0 Version Date: 28 AUG 14 Page 21 of 57

Five study visits will occur at Screening/Baseline (Day 1; Visit 1), Day 6 (Visit 2), Day 14 (Visit 3), Day 28 (Visit 4), and Day 56 (Visit 5). On Day 3, subject will be contacted by phone. Screening data will be reviewed to determine subject eligibility. Screening can occur on Day 1 prior to the start of study drug or within seven (7) days prior to Day 1. If Screening takes place prior to Day 1, then on Day 1, in order to reconfirm eligibility, an abbreviated physical exam, spirometry and a urine pregnancy test for females must be completed prior to dosing on Day 1. Subjects who meet all inclusion criteria and none of the exclusion criteria will be eligible for the study.

Subjects will be permitted to remain in the clinical research center for the full five (5) days of continuous infusion at the discretion of the investigator. During each day of the infusion and for two subsequent days (Day 1 to Day 8), the subject will be instructed to consume at least two (2) liters of fluid. Calcium, BUN and creatinine may be checked more frequently at the discretion of the investigator.

All subjects who had the study drug infusions started will be considered evaluable for safety and efficacy analyses. Incidence of AEs will be monitored during the trial.

Total duration of subject participation will be up to 63 days. Additional data regarding long-term health impact may be ascertained through the CF Foundation National Patient Registry with optional patient consent.

5 CRITERIA FOR EVALUATION

5.1 Primary Efficacy Endpoint

Difference between treatment groups in the proportion of subjects with a 5% or greater relative change in FEV₁ (liters) from baseline to Day 28

5.2 Secondary Endpoints

- Difference between treatment groups in safety parameters including the incidence of AEs, changes in clinical safety labs, and hospitalizations through the end of follow-up
- Difference between treatment groups in the change in pulmonary function parameters from baseline through end of follow-up including relative change in FEV₁ (liters), absolute change in FEV₁ (liters) and in FEV₁ % predicted, and change in FVC (liters and % predicted)
- Difference between treatment groups in the change in sputum *P. aeruginosa* density based on quantitative cultures from baseline through end of follow-up
- Difference between treatment groups in the emergence of other CF pathogens, including gallium-resistant *P. aeruginosa*, from baseline through end of follow-up
- Difference between treatment groups in the change in the CFRSD-CRISS from baseline through end of follow-up
- Determination of the steady state concentration (Css) and elimination half life $(t_{1/2\beta})$ in those subjects receiving IV gallium
- Difference between treatment groups in the change in blood inflammatory markers from baseline through end of follow-up
- Difference between treatment groups in the rate of antibiotic usage including IV, oral, and inhaled for an acute indication from baseline through end of follow-up
- Longitudinal trends in clinical features and CF pathogens following treatment through the CF Foundation National Patient Registry

Version 2.0 Version Date: 28 AUG 14 Page 22 of 57

Protocol Number: GALLIUM-IP-13 Confidential

6 SUBJECT SELECTION

6.1 Study Population

Subjects with a diagnosis of CF who meet the inclusion and do not meet the exclusion criteria will be eligible for participation in this study.

6.2 Inclusion Criteria

- 1. Greater than or equal to 18 years of age at Screening
- 2. Documented chronic colonization with *P. aeruginosa* defined as identification in two sputum or oropharyngeal cultures within the year prior to Day 1
- 3. Documentation of a CF diagnosis as evidenced by one or more clinical features consistent with the CF phenotype **and** one or more of the following criteria:
 - a. sweat chloride \geq 60 mEq/liter by quantitative pilocarpine iontophoresis test (QPIT)
 - b. two well-characterized mutations in the cystic fibrosis transmembrane conductance regulator (CFTR) gene
 - c. Abnormal nasal potential difference (NPD; change in NPD in response to a low chloride solution and isoproteronol of less than -5 mV)
- 4. $FEV_1 \ge 25$ % of predicted value at Screening
- 5. Able to expectorate sputum
- 6. Serum liver function tests ≤ 2.5 x upper limit of normal at Screening
- 7. Serum urea nitrogen (BUN) ≤ 1.5 x upper limit of normal at Screening
- 8. Serum creatinine $\leq 2.0 \text{ mg/dl}$ and $\leq 1.5 \text{ x upper limit of normal at Screening}$
- 9. Hemoglobin \geq 9 g/dl, platelets \geq 100,000/mm³, and white blood cells (WBC) \geq 4,500/mm³ at Screening
- 10. Ionized calcium ≥ lower limit of normal at Screening
- 11. Written informed consent obtained from subject or subject's legal representative, able to communicate with the Investigator and comply with the requirements of the protocol
- 12. If female and of childbearing potential, must have a negative pregnancy test on Day 1 prior to receiving study drug
- 13. If female and of childbearing potential, is willing to use adequate contraception for the duration of the study through Visit 5, as determined by the investigator
- 14. If male and able to father a child, is willing to use adequate contraception for the duration of the study through Visit 5, as determined by the investigator
- 15. Clinically stable with no significant changes in health status within 14 days prior to Day 1

6.3 Exclusion Criteria

- 1. Use of inhaled antibiotics within seven days prior to Day 1
- 2. Unable or unwilling to withhold use of chronic inhaled antibiotics through Day 28

Version 2.0 Version Date: 28 AUG 14 Page 23 of 57

- 3. Use of intravenous, inhaled, or oral antibiotics for an acute indication within 14 days prior to Day 1
- 4. Use of bisphosphonates within seven days prior to Day 1
- 5. History of osteoporosis (defined as the most recent dexa scan with a T-score \leq -2.5 with the dexa scan performed within the five years prior to screening)
- 6. Lactating female
- 7. Known sensitivity to gallium
- 8. Use of any investigational drug and/or participated in any interventional clinical trial within 28 days prior to Screening
- 9. Presence of a condition or abnormality (e.g., pre-existing heart disease) that in the opinion of the site investigator would compromise the safety of the subject or the quality of the data

7 CONCURRENT MEDICATIONS

All subjects should be maintained on the same medications throughout the entire study period, as medically feasible, with no introduction of new chronic therapies.

7.1 Allowed

Standard therapy for CF is allowed except for treatments noted in the exclusion criteria described above and as noted in the prohibited medications section below. Ongoing chronic treatment (>30 days prior to Day 1) with oral antibiotics, including azithromycin, is allowed. Treatment for pulmonary exacerbations and as required for acute care is allowed, including acute oral, inhaled and IV antibiotics. Physicians are encouraged to prescribe acute antibiotic therapy only in the presence of symptoms.

7.2 Prohibited

The following medications are prohibited within seven days prior to Day 1 through Day 28:

- inhaled chronic antibiotics
- bisphosphonates

The use of nonsteroidal anti-inflammatory drugs (NSAIDs) and aspirin is prohibited from Day 1 through 24 hours after the study drug infusion is stopped (e.g., Day 7 for subjects that complete the entire course of study drug).

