10.5 Visit 4 (Day 28 +/- 3 days)

- 1. Administer CFRSD-CRISS.
- 2. Record any AEs.
- 3. Record changes to concomitant medications.
- Record weight.
- 5. Perform complete physical examination.
- 6. Perform and record vital signs.
- 7. Perform and record oximetry.
- 8. Perform and record spirometry.
- 9. Collect blood for clinical laboratory tests (hematology and serum chemistries), gallium and iron levels, and cytokine and chemokine testing.
- 10. Collect urine for urinalysis.
- 11. Collect blood or urine for pregnancy test (if female of child-bearing potential).
- 12. Collect expectorated sputum for culture and gallium and iron levels.

Version 2.0 Version Date: 28 AUG 14 Page 35 of 57

13. Schedule subject for Visit 5.

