15.1 Data Sets Analyzed

Intent-to-Treat Population: All subjects who are randomized and has study drug infusion started will comprise the intent-to-treat (ITT) population. The ITT population will be analyzed for the primary and secondary endpoint analyses and will comprise the safety population used for all safety analyses.

Per Protocol Population: Subjects in the ITT population who have no protocol violations, received no bisphosphonates or inhaled chronic antibiotics from 7 days prior to Day 1 through

Version 2.0 Version Date: 28 AUG 14 Page 40 of 57

Day 28, and received gallium infusion for at least five sequential days. The per protocol population will be used in the sensitivity analyses of the primary and secondary endpoints.

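### As written, the restriction on chronic inhaled antibiotics and the matching per protocol condition stop at Day 28, but the primary FEV₁ and sputum culture at Visit 4 may be taken up to Day 31

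*Protocol*

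**What the plan says.** The restriction appears in three places in the protocol, each time with the same end.

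- Section 7.2, for inhaled chronic antibiotics and bisphosphonates: "The following medications are prohibited within seven days prior to Day 1 through Day 28".
- Section 6.3, exclusion criterion 2: "Unable or unwilling to withhold use of chronic inhaled antibiotics through Day 28".
- The synopsis repeats both.

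The per protocol population (section 15.1, and the synopsis in similar words) has a parallel condition: its members "received no bisphosphonates or inhaled chronic antibiotics from 7 days prior to Day 1 through" Day 28. Section 13 counts use of a prohibited concomitant medication as a violation.

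The primary endpoint in section 5.1 is "Difference between treatment groups in the proportion of subjects with a 5% or greater relative change in FEV₁ (liters) from baseline to Day 28". The Day 28 value comes from the visit headed "10.5 Visit 4 (Day 28 +/- 3 days", and Appendix 1 gives the same window. That visit's list includes "Perform and record spirometry" and "Collect expectorated sputum for culture and gallium and iron levels".

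Section 7 adds a general rule: "All subjects should be maintained on the same medications throughout the entire study period, as medically feasible, with no introduction of new chronic therapies".

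**The concern.** The end of the restriction and the timing of the measurement do not match. The restriction ends on a stated day, while the measurement may fall up to three days later. On the plain wording, a subject may resume a withheld inhaled antibiotic on Day 29, attend Visit 4 on Day 31 and comply with sections 6.3 and 7.2. Because the per protocol condition has the same end, that population keeps the subject as well. It is the sensitivity population that would ordinarily be expected to leave such measurements out.

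Two results are exposed. One is the FEV₁ responder comparison, which is the primary endpoint. The other is the quantitative *P. aeruginosa* culture. Appendix 1 schedules microbiology sputum only at baseline, Visit 4 and Visit 5, and the Visit 3 sputum is for gallium and iron levels only. Visit 4 is therefore the only post-baseline culture that the restriction could cover.

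If some subjects in both arms are measured after resuming an antibiotic, the likely effect is a smaller difference between arms.

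**Working it through.** **Dates.** The window is 28 − 3 = Day 25 to 28 + 3 = Day 31, which is seven permitted days. The last restricted day is Day 28. Days 29, 30 and 31 are uncovered: 3 of 7 permitted days (42.9%). If a Day 29 visit takes place before any dose that day, 2 of 7 (28.6%) are exposed. These are shares of permitted days. The protocol does not say how visits spread over them.

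**The plan's own power figure.** Inputs from section 15.7 are a 30% placebo responder rate, 60 per group, a detectable difference of 28.3 points, and 30.0 points after 10% attrition (54 per group). Section 15 sets a two-sided 0.05 level. With the pooled-variance normal approximation and no continuity correction,

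power = Φ( [ (p₁ − p₀)√n − 1.96√(2p̄(1 − p̄)) ] / √(p₀(1 − p₀) + p₁(1 − p₁)) ), where p̄ = (p₀ + p₁)/2.

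- n = 60, 30% against 58.3%: 88.7%.
- n = 54, 30% against 60%: 89.1%.

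Both are close to the stated 90%, so the plan's figure is reproduced. The date mismatch changes no sample size figure.

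**Illustration of dilution.** Suppose a share *f* of subjects in each arm is measured after resuming an inhaled antibiotic, and a fraction *c* of those who would not have responded become responders. Neither value is in the protocol; both are assumptions. Then

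- placebo rate = 0.30 + 0.70·f·c
- gallium rate = 0.60 + 0.40·f·c
- difference = 0.30·(1 − f·c)

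With 54 per group:

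| f | c | Placebo | Gallium | Difference (points) | Power |
|---|---|---|---|---|---|
| 0 | – | 30.0% | 60.0% | 30.0 | 89.1% |
| 5% | 10% | 30.3% | 60.2% | 29.8 | 88.7% |
| 20% | 20% | 32.8% | 61.6% | 28.8 | 86.1% |
| 42.9% | 30% | 39.0% | 65.1% | 26.1 | 78.4% |

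The last row is an extreme. It needs visits spread evenly over the window and every late visitor to have resumed before being measured. The loss of power therefore runs from 89.1 − 88.7 = 0.4 points to 89.1 − 78.4 = 10.7 points.

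**Does another rule close the gap?** Section 7 is advisory and bars new chronic therapies. Resuming a regimen that was withheld for the study is not clearly new. Section 13 counts only prohibited medication, and after Day 28 the drug is no longer prohibited. Section 9.1.1 records inhaled, oral and intravenous antibiotics through Visit 5 with dates and indication, but the per protocol definition makes no use of those dates after Day 28.

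**The case against.** The strongest reply is that the protocol also uses Day 28 as a label for Visit 4. Section 4.1 pairs the two, the endpoint formula in section 15.3 speaks of a Day 28 FEV₁, and the pharmacokinetic table in section 9.3 lists Day 28 samples as taken at the visit. If the restriction is read the same way, there is no gap. This reading is possible, and it is why the point is about wording as written and not a proven design flaw. But the restriction does not say so, and the protocol names a visit or event when it means one: contraception runs to Visit 5, and the NSAID rule in section 7.2 itself is tied to the stopping of the infusion. With about twenty sites, two available readings are reason enough to settle the text.

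A reader might infer three stronger things that the documents do not support.

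- *That affected measurements cannot be found.* Section 9.1.1 collects the dates needed. Section 15 also leaves detail and modifications to a statistical analysis plan that is not at hand. Only the protocol's own per protocol definition can be said to keep these measurements.
- *That more placebo subjects would resume, biasing the result against gallium.* Treatment is double-blind and nothing in the protocol indicates different restart rates by arm. Section 7.1 also lets subjects with symptoms receive acute antibiotics at any time, before or after Day 28.
- *That the loss is material.* Restart frequency, visit spread and the effect of at most three days of treatment are all absent from the protocol.

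**Conclusion.** The mismatch stands on the text: an end at Day 28 in sections 6.3, 7.2 and 15.1 and the synopsis, against a primary visit that may fall as late as Day 31 in section 10.5 and Appendix 1. It holds unless Day 28 in the restriction means the visit, which is not stated.

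The consequence is limited. The likely effect is some dilution of the FEV₁ responder difference and of the Visit 4 culture comparison, not a false positive. Its size cannot be determined from the protocol and may be negligible; the 10.7-point loss of power is the extreme of the cases tried and rests wholly on assumed inputs. The point deserves correction because the per protocol set, as defined, would not remove these measurements, and because correcting it costs very little.

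**What to change.** 1. In section 15.1 and the synopsis, define the per protocol condition as no chronic inhaled antibiotics *through the Visit 4 spirometry and sputum collection*, in place of through Day 28. Apply it with the antibiotic dates already recorded under section 9.1.1.
2. Have the sponsor reconcile the end of the restriction in exclusion criterion 2, section 7.2 and the synopsis with the Visit 4 window in section 10.5 and Appendix 1, and state whether Day 28 there means the day or the visit.

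The cost is a short wording amendment with no new data collection. A few subjects may leave the per protocol set; the primary ITT analysis is unchanged. No particular antibiotic rule or visit window is prescribed here. Narrowing the window would be one way to align the dates, but it trades against scheduling of the primary visit, and that choice is the sponsor's.
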